4.7 Vulnerable populations

No vulnerable populations will take part in this study.

4.0 Multiple sites

4.1 Northwestern University will serve as the study site solely responsible for contacting participants and conducting study procedures.

6.0 Incomplete Disclosure or Deception

6.1 N/A. This research will not use incomplete disclosure or deception.

5.0 Recruitment

7.1 Recruitment of Patients

A woman research assistant will perform in-person interviews with participants to ascertain if women is eligible for the study and interested to participant. Women who sign written consent and fill out a registration form will be entered into the study. (n=800) (see attached forms)

8.0 Consent Process

8.1 Written consent will be obtained at the following location: Lynn Sage Breast Center of Prentice Hospital/Northwestern Medicine. (see attached consent document)

8.2. N/A. Non-English speaking participants will not be enrolled in this research.

8.3. Participants who are not yet adults (infants, children, teenagers) will not be enrolled in this research. Participants in structured interviews, who are the age of 18 years or older, will be enrolled in this research. Assent will be required from all participants. The RA will obtain verbal assent from each participant and will be documented. The RA will read the assent script to the participant and will then document the participant's response.

8.4 Cognitively Impaired Adults: Participants will be screened for preexisting conditions that would prohibit their participation due to being over burdened by co-morbid diseases, unable to participate in a conversation at a sixth grade language level due to cognitive impairment (e.g., by a stroke), and unable to speak and read English, inability to see to read a newspaper. Subjects having conditions that contraindicate participation will not be enrolled in this research.

8.5. Adults Unable to Consent: Please see above rationale for excluding Cognitively Impaired Adults.

9.0 Process to Document Consent

9.1. Written consent will be obtained in the changing area of the Lynn Sage Comprehensive Breast Center. (See attached consent document)

10.0 Risks to Participants

10.1. The potential risks to participants are expected to be minimal, if they occur. Subjects will be participating in an educational intervention that may enhance their awareness of their risk of developing skin cancer. All study participants will be provided with an email address

Effect of SSE education delivered during the mammography experience.

and phone number to contact study staff in the event they have concerns. If a subject becomes concerned that they have a suspicious lesion, the control subject will be instructed to make an appointment with their own dermatologist for an examination. The research assistant will communicate other concerns to the PI. In such circumstances, [name] will consult with the patient's own dermatologist and an appropriate referral will be made.

Because of the potential for the educational intervention to help the subject identify melanoma at a stage of development with the best prognosis, we feel that the potential benefits, in reduced morbidity and mortality, to the subject outweigh the risk of potential enhanced anxiety in discovering a suspicious mole. Should subjects report high levels of anxiety a referral for psychological support will be made.

10.2. We do not believe that subjects in this study will be exposed to any risk of physical or psychological harm as a result of either the intervention or research processes. Our measures do not assess individuals at risk of immediately harming themselves (e.g. suicide); therefore we will not have to screen the data to potentially intervene with individuals who may be a risk to themselves.

10.3. N/A. There are no anticipated risks to others who are not participants.

11.0 Potential Benefits to Participants

Because of the potential for the educational intervention to help the subject improve their ability to detect melanomas in the early and potentially curable phase, they will reduce their risk of death from melanoma. We feel that the potential benefits in reduced morbidity and mortality to the subject outweigh the risk of potential enhanced anxiety in discovering that they are at risk to develop another melanoma. Should subjects report high levels of anxiety, a referral for psychological support will be made.

The knowledge to be gained by the proposed study is key to the evaluation of the long-term benefit of skin self-examination. By evaluating means of encouraging and facilitating regular skin self-examination, the applicants believe that it will be possible to determine if the educational intervention that can be used in mammogram facilities, which would be beneficial if brought into widespread use.

12.0 Financial Compensation

12.1 N/A. Participants will receive a \$10 Amazon gift card for participation in the second survey (telephone call/REDCap one month after mammogram visit) and an additional \$10 Amazon gift card for completing a third survey (REDCap) three months after the mammogram.

13.0 Provisions to Protect the Privacy Interests of Participants

13.1. This research includes provisions for protecting the privacy of participants. Study interactions will take place in person. The research team will make every effort to address the questions and concerns of potential and current participants.

Steps will be taken to ensure that the participants feel at ease. To reduce the sense of intrusiveness a subject may experience in response to survey questions, subjects will be informed that they may decline to provide any information they do not wish to disclose. The

Effect of SSE education delivered during the mammography experience.

information being collected is limited to only the minimum amount of data necessary to accomplish the research purposes.

13.2. The research team will be permitted to access study-related, subject-reported information and the EMR of subjects who have a visit with the dermatologist for a concerning mole. The database will have deidentified data.

14.0 Data Analysis

14.1. This convenience sample of women undergoing screening mammography will all receive education either as a brochure and a 1-week reminder or as only the brochure. Demographic characteristics of the two groups will be examined using means and standard deviations (age) and counts and percentages for all categorical variables. Primary outcomes of SSE performance, biopsy, and diagnoses will be compared using Chi-square tests of association or Fisher's exact tests where sample sizes were restrictive. Due to the skewed nature of the anxiety scale, a Wilcoxon rank sum test will be used to compare anxiety, the secondary outcome, in the two groups. Descriptive statistics will be performed for the tertiary outcome of dissemination.

15.0 Confidentiality and Data Management:

1. There are no biological specimens. All of the following data is collected in person consent and responses to structured interviews and focus groups.
2. Our systems are guarded against outside entry by Northwestern's own firewall supporting 128-bit encryption. This level of encryption provides the highest level of protection against hackers, computer break-ins, etc. All data is deidentified. Experienced research assistants will be employed and will receive training that includes emphasis upon the importance of confidentiality of information, and all personnel on the project will complete the required NIH training in the protection of human research participants.
3. Data will be retained in separate locked file cabinets and on computers with restricted and password protected access, without links to the master code list. All data based on the research will be reported in aggregate form. No individual respondents will be identified. Electronic data will be maintained in a study specific database on the server of the Department of Dermatology at the Feinberg School of Medicine. Paper-based files will be kept in a locked cabinet in a locked room within the Northwestern University Department of Dermatology research offices. Identifiable data will be kept separate from the case report forms and source documents. Data gathered as a result of this study are available to inspection on request by Food and Drug Administration or other government regulatory agency auditors, and the Northwestern University Institutional Review Board (IRB).
4. Only approved research personnel will have access to the stored data. The PI is ultimately responsible for receipt and transmission of the data. As per Department of Dermatology protocol, data will be retained indefinitely after the completion of the study.
5. All data and other information in this study will be maintained confidentially. In order to protect against risks posed by a potential loss of confidentiality, we will take the following steps: First, subjects will be assured they are free to refrain from answering any questions they do not wish to answer. Secondly, all data will be identified only by a unique subject

Effect of SSE education delivered during the mammography experience.

number. All data is recorded by a study number, which preserves the confidentiality of the information.

6. Please refer to Section 15.0 for the data analysis plan, which includes statistical procedures.

15.1 Data Monitoring Plan to Ensure the Safety of Participants:

As previously described, all participants are encouraged to contact the PI, [name] at Northwestern, to report complaints or adverse events. A telephone number and email address will be given to patients to contact [name] if they have any concerns or increased anxiety, or if they become worried about developing skin cancer. Instructions for reporting adverse events and complaints, as well as for contacting the Investigators, are included in the consent documents and on all contact information provided to participants through the course of the study. Any significant adverse events will be reported to NIH in addition to the local IRB, in compliance with federal regulations.

Our measures do not assess individuals at risk of immediately harming themselves (e.g., suicide); therefore, we will not have to screen the data to potentially intervene with individuals who may be a risk to themselves.

[name] has been a board certified physician for over three decades and has conducted a NCI funded R01 of a similar nature. We will notify the Northwestern University IRB, our project officers, and NCI within 24-48 hours of any serious adverse event. We will provide an annual report to the NCI Project Officer summarizing all adverse events, should any arise.

16.0 Data and if applicable, Specimen Banking Not applicable.

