1.0 Purpose of the Study

The proposed study is the second phase of a project assessing the feasibility and effectiveness of enhancing the early detection of melanomas among women, who are engaging in health promotion by having mammograms. The initial phase of the project framed risk messages, developed posters and brochures with the input provided by women undergoing screening mammograms, and assessed the feasibility of delivering the program during the mammogram visit at the Lynn Sage Comprehensive Breast Center of Northwestern Medicine/ Prentice Women's Hospital. Now, we seek to evaluate performance of skin self-examination (SSE) by women, who receive information during their mammogram appointment, and follow-up with dermatology for a melanoma screening examination.

In the second phase, a more intensive intervention in which women will not only receive information about SSE, but will also receive a reminder to perform SSE one week after the screening mammogram and information on how to schedule an appointment with dermatology will be provided. The number of women who perform SSE at home and find a concerning mole (lesion), number who see a dermatologist, and number who have a concerning lesion biopsied will be compared in two arms of the study 1) women who receive the intensive intervention 2) women who receive the informational brochure about SSE alone.

Our hypothesis is that women who receive more the intensive educational intervention will be more likely to perform SSE at home and schedule a follow-up dermatologist appointment as compared to those who receive the information brochure alone. This project builds upon [name]'s successful SSE training program for melanoma patients that resulted in patients' accurate evaluations of suspicious lesions relative to dermatologists' skin examinations.⁴

The study aims are as follows:

1. Assess whether SSE education introduced during routine screening mammography encourages women to implement SSE at home, find concerning lesions, and seek follow-up with a dermatologist.
2. Assess the effectiveness of additional reminders to perform SSE and providing information on how to schedule follow-up with a dermatologist on participant performance of SSE with identification of a concerning lesion or scheduling a screening examination with a dermatologist without performing SSE.

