A research assistant will be present at the mammography center to collect consent, telephone numbers, iPhone model information, and email addresses to have women sign onto REDCap to complete a survey. A telephone survey will be administered to each woman enrolled in the study in both groups (N=800) one month after the mammogram asking if she performed a SSE at home and whether a follow-up with dermatology was made. An anonymous REDCap survey may be used in place of the telephone call, depending on participant's preferred method of contact preference. Then, three months after the screening mammogram, an anonymous <2 minute REDCap survey will be sent via email to each woman enrolled in both groups to ascertain the number of women who identified that they were at increased risk for melanoma (history of sunburn, history of indoor tanning >10+sessions, family or personal history of skin cancer), performed a SSE at home, found a concerning lesion, made a follow-up appointment with a dermatologist, and had any concerning lesions biopsied. If participants do not complete the REDCap survey in 2 weeks, they will be called and surveyed via telephone. We anticipate a 20% attrition rate (Fig 3). Participants will be offered a \$10 Amazon gift card in appreciation of completing the one month survey and an additional \$10 for completing of a second REDCap survey three months after the mammogram visit.

Effect of SSE education delivered during the mammography experience.

Fig 3. CONSORT diagram for two arms of study

Effect of SSE education delivered during the mammography experience.

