3.3 Research procedures and activities

Follow-Up

1 week after the mammogram, RA will contact participants in group 1 via their preferred method to remind them to perform SSE and schedule a dermatologist appointment if they find a concerning mole. (see attached telephone script)

1 month after the mammogram, the RA will call participants in group 1 and administer a survey to see if they checked their skin and/or made an appointment with a dermatologist.

Effect of SSE education delivered during the mammography experience.

(see attached telephone script) An anonymous REDCap survey may be used in place of the telephone call, depending on participant's preferred method of contact preference.

The survey questions are as follows:

1. Did you read the brochure?
 Yes No
2. Did you check your skin? (If no, please proceed to question #4)
 Yes No
3. If yes, did you notice any concerning moles?
 Yes No
4. If no, will you consider checking your skin in the future?
 Yes No
5. If you found any concerning moles, did you make an appointment to see a dermatologist?
 Yes No

If no, do you intend to do so in the near future?

6. Did you share the brochure with anyone else?
 Yes No
7. If yes, who did you share it with:
 - a) A relative: son, daughter, father, mother, sister, brother
 - b) A friend : woman, man
 - c) Someone I work with: woman, man

REDCap Survey

3 months after the mammogram, an anonymous REDCap survey will be emailed to each woman enrolled in both groups. If participants do not complete the REDCap survey in 2 weeks, they will be called and surveyed via telephone. The following items with relevance to the research:

1. Do you have a history of sunburn? Yes/No
2. Do you have a history of more than 10 indoor tanning sessions? Yes/No
3. Do you have a personal or family history of melanoma? Yes/No
4. Have you ever performed a skin self-examination prior to your most recent mammogram? Yes/No

Effect of SSE education delivered during the mammography experience.

5. Did you perform a skin self-examination after your most recent mammogram?
Yes/No
If no, then go to item 8.
6. Did you find a concerning mole? Yes/No
7. If you found a concerning mole, did you make an appointment to see a dermatologist? Yes/No
8. If you did not perform a skin self-examination, did you still make a follow-up appointment to see a dermatologist for a skin examination? Yes/No
9. Have you had an appointment with a dermatologist yet? Yes/No

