3.4 Measures

The number of women with risk factors for melanoma, who performed SSE after the screening mammogram, who found a concerning mole, who saw dermatology, who had a concerning lesion biopsied in each group will be analyzed by descriptive statistics. The difference in proportions of women who 1) performed SSE 2) saw a dermatologist in the educational intervention group from the intensive intervention group will be compared using a χ^2 test. If the woman responded “yes” to follow-up in dermatology, a chart review of the electronic medical record will be performed to assess whether any lesions were biopsied and pathology of the concerning lesions. The accuracy of the woman’s selection of a concerning lesion will be assessed by examining the correspondence rate between the woman’s assessment during SSE and the dermatologist. The overall correspondence rate will be calculated with a random intercept-only mixed logistic regression model. The statistical analysis will be performed by [name], MPH.

Online data

REDCap survey (see page 8 above)

Approvals required

Effect of SSE education delivered during the mammography experience.

[name] obtained permission for this research to be conducted in the Lynn Sage Comprehensive Breast Center of Northwestern Medicine/Prentice Women's Hospital

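### Sections 1.0, 3.4 and 14.0 give conflicting outcome sets: 14.0 names three primaries with no deciding rule and omits dermatology follow-up

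*Combined protocol and SAP*

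**What the plan says.** Section 1.0 gives three statements of what is compared. Its description of the second phase lists SSE with a concerning lesion found, seeing a dermatologist, and biopsy. Its hypothesis is that intensive-arm women will be "more likely to perform SSE at home and schedule a follow-up dermatologist appointment as compared to those who receive the information brochure alone". Its Aim 2 concerns "performance of SSE with identification of a concerning lesion or scheduling a screening examination with a dermatologist without performing SSE".

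Section 3.4 (Measures) says that the numbers of women "who had a concerning lesion biopsied in each group will be analyzed by descriptive statistics", and applies a chi-square test to "The difference in proportions of women who 1) performed SSE 2) saw a dermatologist". It labels nothing as primary.

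Section 14.0 says "Primary outcomes of SSE performance, biopsy, and diagnoses will be compared using Chi-square tests of association", with Fisher's exact test where numbers are small. Anxiety is the secondary outcome and dissemination the tertiary one. Dermatology appointments and visits are not mentioned.

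Section 3.1 (Study Design, Phase 2) says that the 3-month survey will establish how many women "performed a SSE at home, found a concerning lesion, made a follow-up appointment with a dermatologist, and had any concerning lesions biopsied". In the survey itself (Section 3.3), women who did no SSE are routed past the lesion questions ("If no, then go to item 8"). Item 7 reads "If you found a concerning mole, did you make an appointment to see a dermatologist". Item 8 asks about booking only of women who did no SSE. Item 9 asks whether a visit has taken place.

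**The concern.** The two analysis sections cannot both be followed. Biopsy is descriptive in one and a tested primary in the other. The dermatology visit is tested in one and absent from the other. The plan states no significance level, does not say whether one, any or all of the three primaries must succeed, and gives no rank or test to Aim 2's outcome. The decisive result could therefore be picked after the data are seen, from outcomes that need not move together. Half of the hypothesis, dermatology follow-up, has no place in the section that defines the primary analysis.

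The survey gap bears on the scheduling half of the hypothesis only. It does not touch the test of having seen a dermatologist, which item 9 supplies.

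**Working it through.** **1. Outcomes side by side.**

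| Outcome | 1.0 list of comparisons | 1.0 hypothesis | 1.0 Aim 2 | 3.4 | 14.0 |
|---|---|---|---|---|---|
| SSE performed | only with lesion found | yes | only with lesion found | chi-square | primary, tested |
| SSE with lesion found | compared, no test named | – | part | descriptive | absent |
| Appointment made | – | yes | part (if no SSE) | absent | absent |
| Saw a dermatologist | compared, no test named | – | – | chi-square | absent |
| Biopsy | compared, no test named | – | – | descriptive | primary, tested |
| Diagnoses | – | – | – | chart review, no test between arms | primary, tested |

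Only SSE performance appears in the hypothesis, 3.4 and 14.0. The cross-reference in Section 15.0 (item 6) does not settle the matter: it points to 15.0 for the analysis plan, but the plan is in 14.0.

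**2. Error rate if any one primary sufficed.** The documents give no alpha, so 0.05 two-sided per test is assumed. No rates are given either, so those below are also assumptions. Respondents per arm: 400 × (1 − 0.20) = 320, from 3.1, treated as independent.

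- Bound under any dependence: 3 × 0.05 = 15%.
- Independent tests at full size: 1 − 0.95³ = 14.3%.
- For rare outcomes the tests fall below nominal size. With null rates of 2% (biopsy) and 1% (diagnoses), exact enumeration gives Fisher sizes of 0.0240 and 0.0134: 1 − 0.95 × 0.9760 × 0.9866 = 8.5%. With Fisher only where expected counts are below 5, the sizes are 0.0466 and 0.0157: 1 − 0.95 × 0.9534 × 0.9843 = 10.8%.
- At 1% and 0.5% the same two calculations give 6.5% and 6.7%; at 10% and 5%, 11.4% and 14.3%.
- If all three must succeed, there is no inflation.

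**3. Power of the possible deciding rules.** Assumed rates: SSE 30% vs 40%, appointment 20% vs 30%; 320 per arm; normal approximation, power = Φ[(Δ − 1.96·SE₀)/SE₁].

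- SSE at 0.05: SE₀ = √(2 × 0.35 × 0.65/320) = 0.0377; SE₁ = √((0.21 + 0.24)/320) = 0.0375; power 0.757.
- Appointment at 0.05: SE₀ = √(2 × 0.25 × 0.75/320) = 0.0342; SE₁ = √((0.16 + 0.21)/320) = 0.0340; power 0.833.
- Both must succeed: 0.757 × 0.833 = 0.631 if independent; between 0.757 + 0.833 − 1 = 0.590 and 0.757 under any dependence.
- Either suffices (Holm), at least one: powers at 0.025 are 0.660 and 0.753, so 1 − 0.340 × 0.247 = 0.916 if independent.

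**4. Booking gap in the 3-month survey.** A woman who did SSE, found nothing, booked and has not yet attended is recorded nowhere as having booked. Missed share = SSE rate × 0.9 × 0.20 × (1 − share already attended), assuming 10% find a mole and true booking is 20% in both arms. With SSE at 40% vs 30% and nobody yet attended: 0.072 vs 0.054, a spurious difference of 1.8 points (0.66 of its standard error of 0.0272). If 80% have attended: 0.0144 vs 0.0108, or 0.4 points. If all have attended: zero. The EMR paragraph adds to the confusion, because it treats a yes to item 9 (visit had) as an appointment made.

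**The case against.** The strongest reply is that this is a small behavioural study with one outcome shared by the hypothesis and both analysis sections, so the defect is one of wording. That much is true, and it shows that the repair is easy. It does not remove the contradiction over biopsy and dermatology visits, or supply a deciding rule.

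Five stronger readings are tempting, and the documents do not support them.

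- A reader might infer that the trial runs a false-positive risk of 14 to 15%. That holds only if any one success counts, which the plan does not say. Diagnoses would also come largely from biopsies, and such positive dependence lowers the figure below 14.3%.
- A reader might infer that Aim 2 is a composite that can fall while SSE rises. The wording can equally mean two separate outcomes. Even as a composite (SSE × find + (1 − SSE) × book), the direction depends on assumed rates. With SSE at 40% vs 30%: 16% vs 17% if 10% find a lesion and 20% of non-performers book; 14% vs 13% if these are 20% and 10%; 22% vs 17% if 10% find a lesion and booking is 30% vs 20%.
- A reader might infer that biopsy and diagnoses are too rare to decide anything. Fisher power at 320 per arm is 25% for 2% vs 4% but 87% for 5% vs 12%, and no rates are given.
- A reader might infer that a between-arm comparison of biopsy is peculiar to 14.0. Section 1.0 also lists one.
- A reader might infer that appointments must be a deciding outcome because the card targets them. Section 3.1 places cards in all eight changing rooms, and 14.0 describes the arm difference as the reminder alone, so the card is not clearly a contrast between arms.

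The anxiety scale in 14.0 is unnamed, but it may be in attachments not shown and forms no part of this point.

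**Conclusion.** The point holds: the outcome sets in 1.0, 3.4 and 14.0 conflict, 14.0 leaves out dermatology follow-up, and nothing says which primary decides. This rests on the text alone and should be settled before outcome data are seen. The size of the error inflation is conditional: none if all three primaries must succeed, at most 15% if any one suffices at an assumed 5%. The survey gap is real but minor, at most 1.8 points under the assumptions shown and zero once all bookers have attended.

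**What to change.** **Outcome list.** Use one list in 1.0, 3.4 and 14.0, fixed before data are seen.

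- Deciding primary: SSE performed by 3 months (item 5). It is the one outcome that the hypothesis and both analysis sections share, and it needs no multiplicity rule.
- Key secondary, added to 14.0 with chi-square tests: appointment made (item 8, reworded as below) and saw a dermatologist (item 9).
- Secondary: SSE with a lesion found (items 5 and 6), and Aim 2's outcome, stating whether it is one composite or two outcomes. As a composite it is yes to items 5 and 6, or no to item 5 and yes to item 8.
- Non-deciding, in both 3.4 and 14.0: biopsy and diagnoses, with 95% confidence intervals.

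If the sponsor prefers SSE and appointment made as joint deciding outcomes, 14.0 should say whether both must succeed (each at 0.05) or either suffices (Holm, 5% overall).

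**Survey.** Reword 3-month item 8 so that every woman is asked whether she has made a dermatology appointment for a skin examination since the mammogram. Keeping it as item 8 leaves the skip from item 5 and the EMR reference to item 9 correct. Make the same change to question 5 of the 1-month survey, which is also limited to women who found a mole. In the EMR paragraph, change *made* to *had*.

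**Cost.** Wording changes, one near-repeat question for women who found a mole, and loss of primary status for biopsy and diagnoses. Under the assumed rates, power is about 76% with SSE as sole primary and about 63% if both outcomes must succeed and are independent.

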3.0 Procedures Involved

3.1 Study Design

Phase 1: *Delivery of educational SSE program.*

Each of the eight changing rooms of the Lynn Sage Comprehensive Breast of Northwestern Memorial Hospital will be equipped with a poster, brochures (Fig 1 and Fig 2) and cards with information about obtaining an appointment with a dermatologist for concerning skin lesions.

A woman research assistant will obtain consent to participate in the research and review of medical information, collect contact information and if the woman owns an iPhone X, 8+ or 8, and ensure receipt of an informational brochure. Women will be asked if they own an iPhone X, 8+ or 8 to assess the prevalence of these specific phones in the population of interest. These iPhones models are of particular interest to the research team as they offer superior image quality compared to older models. If a woman has this type of phone, she will be asked about her experience using it to take close-up pictures. The woman will be asked her preference for being contacted by email, telephone, or text message. The two arms of the study will be delivered on different weeks. During weeks 1,3,5 and 7 of the study period 400 women will be given brochures and a card with information on scheduling dermatology follow-up prior to check-out (Group 1), (Fig 3). During weeks 2, 4, 6 and 8 of the study period, 400 women will be given brochures to perform SSE at home and proceed to check-out of the mammogram area (Group 2). The women in Group 1 will also receive a reminder about performing a SSE one week after their mammogram visit via phone call,

Effect of SSE education delivered during the mammography experience.

email or text message. One month after the mammogram visit both groups will be called and surveyed to see if they checked their skin and/or made an appointment to see a dermatologist. Three months after the mammogram, both groups will be asked to participate in a complete survey (either via REDCap or telephone), including whether the women followed up in dermatology and if any concerning lesions were biopsied.

Fig 1. SSE Poster

[figure not shown]
[figure not shown]

Fig 2. Cover of SSE

[figure not shown]

Phase 2: Assessment of SEE Implementation

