3.2 Informed Consent, Participant Surveys, and Educational Intervention

As patients wait to have the mammogram, they will be screened for eligibility. Following completion of the mammogram, patients will return to the changing room and put on their clothing. After exiting the changing room in the Lynn Sage Comprehensive Breast Center of Northwestern Medicine/Prentice Women's Hospital and as they are preparing to leave, a research assistant (RA) will interview potential participants to acquire a randomly selected convenience sample of eligible participants (n=800). Participants will be invited to complete a survey that will assess knowledge of melanoma and the risk of developing a melanoma. They will be provided with a consent form and the research study will be discussed, questions will be invited and then they will be asked to sign a consent form and to fill out a registration form containing contact information. (see attached)

The complete survey includes general demographic items such as age, education, household income, race and ethnicity. The survey questions are as follows:

1. During your visit for mammography, did you notice any information about checking your skin for melanoma?

Yes No

2. Did you think this applied to you?

Yes No

3. If no, why not? (open ended)

4. If yes, why? (open ended)

5. Did you check your skin? (If no, please proceed to question #7)

Yes No

6. If yes, did you notice any concerning moles?

Yes No

7. If no, will you consider checking your skin in the future?

Yes No

8. If you found any concerning moles, did you make an appointment to see a dermatologist?

Yes No

The RA will record the responses.

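### Arms alternate by calendar week, but the between-arm tests treat women as independent; for common outcomes such as SSE performance this overstates certainty if weeks differ beyond chance

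*Combined protocol and SAP*

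**What the plan says.** **Allocation.** Section 3.1 Study Design: "The two arms of the study will be delivered on different weeks". For Group 1, the intensive arm: "During weeks 1,3,5 and 7 of the study period 400 women will be given brochures and a card". For Group 2, the brochure-only arm: "During weeks 2, 4, 6 and 8 of the study period, 400 women will be given brochures to perform SSE at home". There are thus eight allocation units, four per arm, and all women enrolled in one week belong to the same arm. The same section expects 20% attrition.

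**Analysis.** Section 14.0: "Primary outcomes of SSE performance, biopsy, and diagnoses will be compared using Chi-square tests of association", with Fisher's exact test as the alternative when numbers are small. Section 3.4 Measures names what will be compared by chi-square: "The difference in proportions of women who 1) performed SSE 2) saw a dermatologist in the educational intervention group", against the intensive group. Anxiety is to be compared by a Wilcoxon rank sum test.

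**What is absent.** The text has no week term, ICC, design effect or cluster-robust variance for any between-arm comparison. The one mixed model, in section 3.4, is for the rate of agreement between woman and dermatologist, not for the comparison of arms. No alpha, power calculation or expected event rate is stated.

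**The concern.** A chi-square test takes its standard error from binomial variation among independent women. Here arm is a property of the week, so any variation between weeks passes directly into the difference between arms. Averaging over more women within a week does not remove it. With four weeks per arm, a few better or worse weeks could produce a difference that the test attributes to the card and reminder.

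This is a matter of standard error, separate from bias. Adjusting for women's characteristics removes only the part of the weekly variation that those characteristics explain. Week cannot be entered as a fixed effect, because week determines arm.

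Aim 2, the effect of adding reminders and scheduling information, rests on this comparison. A significant SSE result from the planned test could not be separated from ordinary weekly fluctuation.

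**Working it through.** There is no sample-size or error-rate figure in the plan to reproduce; only 400 + 400 = 800 can be checked.

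**Inputs from section 3.1 Study Design**
- Women per week: 400 / 4 = 100, if recruitment is even.
- After 20% attrition: 100 × 0.80 = 80 per week, 4 × 80 = 320 per arm, 640 in total.

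**Assumptions (not in the documents)**
- Two-sided alpha of 5%; SSE rate of 40%, so p(1 − p) = 0.24.
- ICC from 0 to 0.02; week effects independent of each other.

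**Formulas**
- Design effect: DE = 1 + (80 − 1) × ICC.
- Actual type I error of the chi-square test: 2 × [1 − Φ(1.96 / √DE)].
- Effective total sample: 640 / DE.
- SD of the true weekly rates: √(0.24 × ICC).

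Example at ICC 0.01: DE = 1 + 79 × 0.01 = 1.79; 1.96 / √1.79 = 1.465; error = 14.3%; effective sample = 640 / 1.79 = 358; SD = √0.0024 = 4.9 points.

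| ICC | SD of weekly rate (points) | DE | Actual type I error | Effective N |
|---|---|---|---|---|
| 0 | 0 | 1.00 | 5.0% | 640 |
| 0.001 | 1.5 | 1.08 | 5.9% | 593 |
| 0.005 | 3.5 | 1.40 | 9.7% | 459 |
| 0.01 | 4.9 | 1.79 | 14.3% | 358 |
| 0.02 | 6.9 | 2.58 | 22.2% | 248 |

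Simulation of eight weeks of 80 women agrees with the error column to within one percentage point. In the same simulations a t-test on the eight weekly proportions (6 df) stayed at about 5% at every ICC shown.

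**Effect of alternation.** The table treats weeks as independent draws. If neighbouring weeks are alike, alternation cancels part of the variation. At ICC 0.01 with first-order autocorrelation of 0.3, 0.5 and 0.7 (assumed), the simulated chi-square error falls from 14% to between 10% and 11%, about 9% and about 7%.

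**Rare outcomes.** With Fisher's test and an assumed 1% event rate, the simulated error is 1.3% at ICC 0, 3.1% at 0.005, 5.9% at 0.01 and 9.8% at 0.02. The weekly t-test is no remedy here. At an assumed 0.2% rate it has zero variance, and so no result, in 28% of runs at ICC 0 and 39% at ICC 0.01.

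**Detectable SSE difference at 80% power**
- Chi-square, women independent: 2.8 × √(2 × 0.24 / 320) = 10.8 points.
- Weekly t-test: (2.447 + 0.906) × √(0.24 / 80 × DE) × √(2 / 4) = 3.353 × 0.0387 × √DE. This is 13.0 points at ICC 0, 15.3 at 0.005 and 17.4 at 0.01.

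**The case against.** The strongest reply is that positive correlation within weeks is assumed, not shown. This is one clinic over eight weeks, education is given woman by woman, and follow-up contacts are timed from each woman's own mammogram. A reader might infer that women in one week share a research assistant. The documents give no weekly rota; they speak sometimes of one assistant and sometimes of several, so that mechanism is possible but undocumented. At ICC 0 the planned chi-square is valid, and at 0.001 the inflation is slight. The larger ICCs also ask a good deal of one clinic: 0.02 implies true weekly rates with an SD of about 7 points. Alternation reduces the inflation further when adjacent weeks are similar.

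All of this stands as a limit on size. It does not justify the test, because nothing in the plan supports an ICC of zero, and a weekly SD of only 3.5 points would nearly double the false-positive rate if weeks are independent.

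A reader might also infer that the error rate fails for every between-arm test. The documents do not support that: section 14.0 provides Fisher's test for sparse data, and for rare biopsies or diagnoses its conservatism can leave the error below 5% at a small ICC.

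**Conclusion.** The planned analysis does not match the unit of assignment, and that follows from the text alone. The practical consequence is conditional: if weeks differ beyond chance, inference on SSE performance and dermatologist visits is too optimistic. Under the stated assumptions the actual error runs from 5% (ICC 0) to 22% (ICC 0.02), with 10% to 14% at ICCs of 0.005 to 0.01, and less than this if adjacent weeks are alike. The true ICC is unknown.

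The conclusion does not extend with the same force to rare biopsy and diagnosis outcomes, and it does not show that any particular result will be false. The mismatch should still be corrected before the arms are compared, because the main hypothesis depends on the affected tests.

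**What to change.** In sections 14.0 (14.1) and 3.4:

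1. For SSE performance and dermatologist visits, make the primary between-arm test respect the week. Use either a t-test on the eight weekly proportions with 6 df, or a logistic model with a random week effect and a small-sample df correction. Report the risk difference with its 95% CI on that basis, and keep the woman-level chi-square as supportive.
2. For rare biopsy and diagnosis outcomes, keep Fisher's exact test, report counts by arm and week, and state that the test ignores week.
3. Keep mammogram week as a variable in the analysis file. This needs an explicit instruction, because the surveys are described as anonymous and the database as deidentified.
4. State the alpha and an assumed ICC or range.

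The work is a change of wording, one retained variable and a few lines of code. The real cost is precision. The detectable SSE difference rises from about 11 points to about 13 even at ICC 0, and to 15 or 17 at ICC 0.005 or 0.01. The week-level test also has a limit of its own: the week order is fixed and not randomised, so it still assumes that weeks are exchangeable, and the report should say so.
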